6.6.5 Modifiers of Outcome and Severity Indicators

Since the range of developmental abilities is narrow in very young infants, it is difficult to define those subjects with pre-existing disabilities. Consequently, syndromes and medical conditions typically associated with developmental disabilities will be identified, to verify equal distribution between treatment groups.

Psychosocial variables including family resources^{91–93} and family functioning^{91, 94} have been consistently associated with outcome following traumatic brain injury. While the relationship between these psychosocial variables and outcome is not as well studied after CA, Bloom (1997) reported that higher socioeconomic status was related to higher cognitive function in both subjects after CA and in controls.⁵³ We plan to control for the impact of these variables in exploratory analyses. Pre-cardiac arrest baseline family functioning will be measured using the General Functioning Scale of the Family Assessment Device (FAD).⁹⁵ This 12 item scale is a self-reported measure with good internal consistency (range of 0.86 – 0.91).^{96, 97} It discriminates well between healthy and poor functioning families.^{91, 98–100}

Additional severity indicators such as medical or surgical interventions (e.g., need for tracheostomy or mechanical ventilation), rehabilitation services received, and the child's location or level of care needed (e.g., acute care hospital, rehabilitation hospital, nursing home or long term care facility, or at home). These data elements will be collected for descriptive purposes, according to the schedule of assessments outlined in Table 2 on page 36.

Table 3: Neuropsychological battery for subjects older than 6 years.

Domain	Test Name	Constructs Measured	Test Variables
Intelligence	WASI	Overall cognitive ability	Full scale IQ
Processing Speed	WISC-Coding or WAIS-Digit Symbol	Graphomotor speed	Number of symbols copied in time limit
Attention	WISC or WAIS-Digit Span	Attention span Verbal working memory	Total number of items recited correctly
Learning and Memory	CVLT-C or CVLT-II ROCF - Recall and Recognition	Verbal learning Verbal memory Visual memory	Number of words recalled in trials 1 to 5 Short term and long term recall Recognition memory Short term and long term recall Recognition memory
Executive Functioning	ROCF - Copy COWA	Visual organization Novel verbal generation	Total accuracy score Total number of words generated
Visual-Motor Functioning	Grooved Pegboard Test VMI	Fine motor dexterity Graphomotor accuracy	Time to place all pegs in the board Total accuracy score

6.6.6 Family Burden

To assess the impact of the child's health status on the family, the Child's Health Questionnaire (CHQ)¹⁰¹ and the young child's version of this measure, the Infant/ Toddler Quality of Life Inventory (ITQOL)¹⁰² will be used. On both measures, scales assessing the impact of the child's health condition on parent activities and the impact of the child's health on the parent's emotional status will be employed. Additionally, in the children 5 and older, a third scale assessing limitations in family activities as a result of the child's health status will also be employed. The total score for each of these scales will be converted to a score from 0-100 to allow for comparability between the two measures. The family activities and emotional burden scales of the ITQOL and CHQ have yielded significant differences between healthy children and those with a variety of disease states^{103, 104} and between healthy children and children following traumatic injury.¹⁰⁵

7 Detailed Study Interventions

The study interventions will begin in the intensive care unit as soon as possible after informed consent is received. Cardiac arrest patients in the emergency department will be expeditiously transferred to the PICU. Therapeutic hypothermia will not be induced in the emergency department. The setting of the patient's study cardiac arrest (IH vs OH) will be identified, after which the patient will be randomized to a study treatment group (hypothermia or normothermia) in the respective THAPCA Trial (THAPCA-OH or THAPCA-IH). The intervention time period covers the cooling, hypothermia, and rewarming time periods and the interval to 120 hours from the time intervention begins for both arms. Temperature control will be implemented with the Blanketrol III cooling unit (if the Blanketrol III is not available or is already in use, a Blanketrol II can be substituted) and appropriate patient size Maxi-Therm Lite mattresses. Temperature control will use the servo-control mode of the Blanketrol III. The Blanketrol III (and the Blanketrol II) cooling unit and blankets are manufactured by Cincinnati SubZero (CSZ), Cincinnati, OH, in accordance with all applicable Federal regulations. The Blanketrol II has been utilized safely in adult and neonatal clinical trials of therapeutic hypothermia (32 to 34 °C), and the Blanketrol III is the most current model. These prior populations represent the extremes of age ranges for the intended THAPCA Trial (Newborns and Adults vs Pediatric age groups). In prior studies there were no reports of significant skin injury or other complications associated with cooling using

Blanketrol II cooling units.

7.1 Hypothermia

Patients randomized to receive therapeutic hypothermia (hypothermia group) will have a target temperature of 33 °C plus or minus 1 °C (32 to 34 °C). Hypothermia will be induced using the Blanketrol III cooling unit and Maxi-Therm Lite blankets placed below and over each patient. No internal cooling procedures or devices will be used (e.g., gastric lavage, intravascular cooling catheter). Based on newborn and adult reports that used the Blanketrol II cooling unit, we expect to achieve the target temperature range within 1 to 4 hours of initiating cooling procedures.^{30, 106} For the NICHD Neonatal study, cooling was achieved within 90 minutes³⁰ and in an adult TBI study, 2.8 hours (1.1 to 4.5 hr range) was reported.¹⁰⁶

For patient safety, dual central temperature measurements will be performed. A temperature sensing esophageal probe and temperature sensing Foley catheter (or rectal temperature probe) will be placed for temperature monitoring prior to initiation of cooling. Please note: the esophageal probe is the preferred primary probe which will be connected to the Blanketrol unit. However, in the event that an esophageal probe is not judged to be feasible, the Foley catheter or rectal probe may be used as the primary probe and the remaining probe will be the secondary probe which will be connected to the bedside monitor. For patient safety, the *lowest* value will be assumed correct if there is a discrepancy in measurements. If there is a discrepancy of greater than 2 °C between the two measurements, the temperature probes should be inspected for proper positioning and function. The patient's temperature will be monitored continuously and recorded every 30 minutes until central temperature is 33 °C. If the patient is 33 degree at the time of therapy initiation, the temperature will be monitored every 30 minutes for at least one hour. Thereafter, the temperature will be recorded every hour until rewarming begins.

The hypothermia group will be sedated with midazolam and fentanyl. Other benzodiazepines and narcotics may alternatively be used at the clinical site's discretion. The hypothermia group will be paralyzed with vecuronium until the therapeutic hypothermia temperature range is achieved. Vecuronium for paralysis will be held after the initial cooling period and utilized only as needed for shivering unresponsive to the sedation/analgesia protocol described in Section 7.5 on page 49.

Once the patient has achieved the goal temperature (32 to 34 °C), the mattress placed on top of the patient may be moved, however, the mattress

underneath the patient will be left in place. Nursing staff will adjust the Blanketrol III unit as needed to maintain a temperature in the goal range. The hypothermia group will then be maintained in the goal temperature range for 48 hours. Rewarming will then occur over approximately 16 hours (0.7 °C every 4 hours) to normothermia (36.0 °C), which should occur at approximately 72 hours after intervention begins. Temperature will again be recorded every 30 minutes during the rewarming period.

From 72 hours or end of rewarming until 120 hours (end of day 5), the hypothermia group will be maintained in the normothermic range (36-37.5 °C) using the Blanketrol III, and temperature will be recorded every four hours. After 120 hours, temperature management will be according to the normal practice of the clinical care team.

7.2 Normothermia

Patients randomized to receive the normothermic control therapy (normothermia group) will have a target temperature of 36.75 (effectively 36.8) plus or minus 0.75 degrees Celsius (36.0 to 37.5 °C). Similar to the hypothermia group, each patient will be placed on a Blanketrol III cooling mattress (Maxi-Therm Lite) set to the appropriate temperature. Once the patient has achieved the goal temperature (36-37.5 °C), it will be maintained with the mattress.

For patient safety, dual central temperature measurements will be performed. A temperature sensing esophageal probe and temperature sensing foley catheter (or rectal temperature probe) will be placed for temperature monitoring. For patient safety, the *highest* value will be assumed correct if there is a discrepancy in measurements. If there is a discrepancy of greater than 2 °C between the two measurements, the temperature probes should be inspected for proper positioning and function. The patient's temperature will be monitored continuously and recorded every 30 minutes until central temperature is 36.8 °C. Thereafter, the temperature will be recorded every hour through 72 hours then every four hours through 120 hours. For study purposes, the temperature measurement closest to the hour should be recorded.

The normothermia group will be sedated with midazolam and fentanyl. Clinical shivering will be treated the same as with the hypothermia group with midazolam and fentanyl dosing as needed. Other benzodiazepines and narcotics may alternatively be used at the clinical site's discretion. See Section 7.5 on page 49 for a detailed description of sedation and neuromuscular blockade therapies.

Throughout the intervention period, nursing staff will adjust the Blanketrol III unit as needed to maintain a temperature in the goal range. The normothermia group will be maintained in the goal temperature range through 120 hours. This corresponds to the hypothermia, rewarming, and normothermia time periods for the hypothermia group. After 120 hours, temperature management will be according to the normal practice of the clinical care team until hospital discharge.

For subjects randomized to the normothermia group with central temperatures below the normothermic range at the time of randomization, slow rewarming to 36 °C at a rate not to exceed 0.5 °C per hour will be initiated. For patients with temperatures greater than 37.5 °C at the time of randomization, the Blanketrol III unit will be used to cool the subject to 37.5 °C. Ibuprofen or other non-steroidal anti-inflammatory drugs that interfere with platelet function are prohibited for use in patients under this protocol. Acetaminophen may be administered in a dose of 10-15 mg/kg if the clinical team determines there exists no contraindication to its use. If body temperature exceeds 38.0 °C in spite of acetaminophen and Blanketrol III cooling, the clinical care team will administer vecuronium (0.1-0.2 mg/kg) once to assist in cooling to normothermia.

7.3 Temperature Monitoring

Central temperature monitoring will be required during this study as alternative methods are not reliable. Core body temperature will be measured at two sites for safety, esophageal and either bladder or rectal temperature. In addition to monitoring subject temperature as described below, the water temperature of the Blanketrol III will be monitored and recorded at the same frequency as the subject central temperatures.

Esophageal probe placement will be in the distal third of the esophagus away from the airway. The appropriate sized esophageal temperature probe should be placed just prior to initiating cooling. Using the upper incisors as the marker, the following formula will be used to calculate the distance to insert the probe: $0.25 \times ht \text{ (cm)} + 4.5 \text{ (cm)} = \text{insertion distance in cm.}$ ¹⁰⁷ Proper position will be determined by chest x-ray. Repositioning will be done as needed.

NOTE: Temperature sensing foley catheters as well as temperature sensing esophageal catheters contain metal and may need to be removed prior to an MRI. Each site will need to establish MRI compatibility of temperature sensing catheters. If data are not available, the catheters will be removed at the time of MRI and replaced after leaving the MRI suite.

Temperature will be monitored continuously and recorded hourly through 72 hours and then every 4 hours thereafter through 120 hours. During the initial time to target temperature (hypothermia or normothermia) it will be recorded every 30 minutes. It will also be recorded every 30 minutes during the rewarming period for the hypothermia group. Temperature management after the initial 120 hours will be according to the usual PICU clinical practice at each site. Review of the minimum and maximum daily temperatures, including the measurement site, will be recorded through 10 days (240 hours).

7.4 Vascular Access

Secure venous access will be required to safely administer fluids and other medications such as inotrope/vasopressor infusions. The standard practice in PICUs is placement of a temporary central venous catheter. A variety of other central venous access type catheters will also be acceptable. A central venous catheter (CVC) may be pre-existing (acute or chronic line such as a Broviac) or peripheral inserted central catheter (PICC line) during the intervention time period so that intravenous fluids and medications may be administered as needed post arrest.

7.5 Management of Sedation and Analgesia

The use of sedatives and analgesia will be as similar as is clinically feasible in the hypothermia and normothermia groups. Previous adult clinical trials utilized midazolam with or without fentanyl for sedation and analgesia. These agents are well known to practitioners in emergency department and intensive care settings where they are commonly utilized for a variety of indications. Midazolam and fentanyl by continuous infusion supplemented by intermittent dosing will be used for the time intervals corresponding to initial cooling, 48 hours of sustained temperature, and 16 hours of rewarming for both groups.

After the period of cooling and rewarming, which will occur at approximately 72 hours in each group, sedation and analgesia use will be at the discretion of the primary clinical team caring for the patient. Information on agents utilized up to 120 hours (end of day 5) will be recorded.

7.5.1 Sedation

Midazolam is the sedative agent recommended, but not required, for use in this study. A loading dose of 0.1 mg/kg (100 mcg/kg) of midazolam will

be administered for both groups at the time the interventions are initiated. This will be repeated as needed to achieve a Ramsay score of at least 5 (sluggish response to light tap). A continuous IV infusion of midazolam at 100 mcg/kg/hr will be initiated and maintained at this rate or greater during the initial 4 hour period corresponding to time to cool in the hypothermia group. If required, up to two additional doses of midazolam 0.1 mg/kg (100 mcg/kg) may be given. The infusion rate can then be increased by 50 mcg/kg/hr as needed to achieve a Ramsay sedation score of 5.

If the Ramsay score is 6 (no response) after the first four hours of the intervention, the midazolam drip will be weaned by 50 mcg/kg/hr to achieve a Ramsay score of 5. Lowest infusion dose in the initial 24 hours will be 50 mcg/kg/hr. After 24 hours, the midazolam infusion may be weaned to off if there is no clinical shivering, patient temperature is in the appropriate target range, and the goal for sedation/analgesia is obtained (Ramsay score of 5).

Other benzodiazepines (e.g., lorazepam) may be used as an alternative to midazolam at the clinical site's discretion. However, the level of sedation should be based on the Ramsay targets outlined here.

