7.5.2 Analgesia

Fentanyl is the analgesic agent recommended, but not required, for use in this study. A loading dose of 2 mcg/kg will be administered for both groups at the time the interventions are initiated. Continuous infusion of fentanyl will begin at 2 mcg/kg/hr and maintained at this rate during the initial 4 hour period corresponding to time to cool in the hypothermia group. If required, up to two additional doses of fentanyl 1 mcg/kg may be given. The infusion rate can then be increased by 1 mcg/kg/hr as needed to achieve a Ramsay sedation score of 5.

If the Ramsay score is 6 (no response) after the first four hours of the intervention, the fentanyl drip will be weaned by 1 mcg/kg/hr to achieve a Ramsay score of 5. The lowest infusion dose in the initial 24 hours will be 1 mcg/kg/hr. After 24 hours, the fentanyl infusion may be weaned to off if there is no clinical shivering, patient temperature is in the appropriate target range, and the goal for sedation/analgesia is obtained (Ramsay score of 5).

Other narcotics (e.g., morphine, remifentanyl) may be used as an alternative to fentanyl at the clinical site's discretion. However, the level of analgesia should be based on the Ramsay targets outlined here.

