7.6 Use of Neuromuscular Blockade

Vecuronium is the recommended, but not required, neuromuscular blocker for the THAPCA Trials. A paralytic loading dose of 0.1-0.2 mg/kg (100-200 mcg/kg) will be administered to patients randomized to hypothermia to facilitate cooling. Repeated doses of vecuronium will be administered as needed to maintain paralysis until the patient is cooled to the therapeutic range (32-34 °C).

Once therapeutic hypothermia is achieved, neuromuscular blockade is not required, except for as needed to control shivering resistant to sedative/analgesic agents and rewarming without clinical shivering. If a cooled patient begins to rewarm above 34.5 °C in spite of the absence of clinical shivering, vecuronium in a dose of 0.1-0.2 mg/kg (100-200 mcg/kg) would be administered immediately, and continued until the patient cools to the therapeutic range (32-34 °C). Neuromuscular blockade may also be used for other aspects of care at the discretion of the primary care team (such as ventilator asynchrony).

Other non-depolarizing agents may be used during cooling and to control shivering based on the above parameters at the clinical site's discretion.

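### The Ramsay 6 weaning rule for midazolam and fentanyl has no exception for neuromuscular blockade, which by itself gives a score of 6

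*Protocol*

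**What the plan says.** Protocol section 7.5.1 starts midazolam at 100 mcg/kg/hr or more and keeps it there for the first four hours. It then directs: "If the Ramsay score is 6 (no response) after the first four hours of the intervention, the midazolam drip will be weaned", in steps of 50 mcg/kg/hr, aiming for a score of 5. Section 7.5.2 has the same trigger for fentanyl, which starts at 2 mcg/kg/hr: "after the first four hours of the intervention, the fentanyl drip will be weaned by 1 mcg/kg/hr to achieve a Ramsay score of 5". For the first 24 hours the floors are 50 and 1 mcg/kg/hr. After that either infusion may be stopped, on conditions that include a Ramsay score of 5. Section 7.5.1 describes 5 as a sluggish reaction to a light tap and 6 as no response.

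Blockade is covered separately. During cooling, section 7.6 says: "Repeated doses of vecuronium will be administered as needed to maintain paralysis until the patient is cooled to the therapeutic range". Once the target is reached, "neuromuscular blockade is not required, except for as needed to control shivering resistant to sedative/analgesic agents and rewarming without clinical shivering". For a cooled child who drifts above 34.5 °C, vecuronium "would be administered immediately, and continued until the patient cools to the therapeutic range". Section 7.6 adds: "Neuromuscular blockade may also be used for other aspects of care at the discretion of the primary care team". In the normothermia arm, if temperature exceeds 38.0 °C despite acetaminophen and surface cooling, section 7.2 says "the clinical care team will administer vecuronium (0.1-0.2 mg/kg) once to assist in cooling to normothermia".

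None of these sections, nor 7.12 or 7.13, says what happens to the Ramsay rule while a child is blocked.

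**The concern.** The Ramsay score reads depth of sedation from a visible response. A blocked child shows none, so the score is 6 at any depth of sedation. The rule then tells staff to reduce both the sedative and the analgesic in a child who cannot move to show distress.

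The shivering pathway shows the problem most clearly. Section 7.1 says "Vecuronium for paralysis will be held after the initial cooling period and utilized only as needed for shivering" that sedation and analgesia have not controlled. So sedation is tried first and found insufficient, vecuronium is added, the score becomes 6, and the text orders sedation reduced. The rule runs backwards for a child who has just been shown to need more.

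What is at stake is a child who regains awareness while paralysed and under-sedated. The trial's inference is not affected.

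**Working it through.** The protocol gives no figure to reproduce. The check is a reading of sections 7.1, 7.2, 7.5 to 7.6 and 7.12 to 7.13 against each other, with simple arithmetic on the stated rates.

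**1. Is the rule qualified?** No. Both wean sentences are directive, and neither mentions blockade. Section 7.5 hands sedation to the clinical team only at about 72 hours, so the rule runs from hour 4 to roughly hour 72.

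**2. Is the score informative under blockade?** The protocol does not say how to score a paralysed child, so this is an inference, but a direct one. A 5 needs a reaction to a tap and a 6 is no response, so a fully blocked child cannot score 5. Weaning toward 5 cannot succeed while the block lasts.

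**3. Is blockade foreseen after hour 4?** Yes, in five situations:

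| Situation | Section | Arm |
|---|---|---|
| Target not yet reached; repeat doses tied to temperature, not time | 7.6 | Hypothermia |
| Shivering resistant to sedation and analgesia | 7.1, 7.6 | Hypothermia |
| Drift above 34.5 °C | 7.6 | Hypothermia |
| Clinical discretion, e.g. ventilator asynchrony | 7.6 | Either |
| Above 38.0 °C despite other measures, one dose | 7.2 | Normothermia |

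For the first situation, section 7.1 expects the target within 1 to 4 hours but cites an adult range of 1.1 to 4.5 hours. The excess over the hold is 4.5 − 4 = 0.5 h.

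**4. Size of one wean step**, as step ÷ current rate:

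| Rates before the step (mcg/kg/hr) | Midazolam | Fentanyl | Cut |
|---|---|---|---|
| Starting rates, 100 and 2 | 100 → 50 | 2 → 1 | 50/100 = 1/2 = 50% |
| Raised once (assumed), 150 and 3 | 150 → 100 | 3 → 2 | 50/150 = 1/3 = 33% |
| Raised twice (assumed), 200 and 4 | 200 → 150 | 4 → 3 | 50/200 = 1/4 = 25% |

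**5. How far can it go?** From the starting rates, the steps available before the floor are (100 − 50)/50 = 1 and (2 − 1)/1 = 1. The next step would be 50 − 50 = 0 or 1 − 1 = 0, which is stopping, and the text reserves that for a score of 5. So from the starting rates a child scoring 6 loses at most one step, before or after 24 hours. From raised rates more than one step is possible, but the protocol gives no Ramsay scoring interval, so the number within one block cannot be computed.

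**6. Scope.** Substitute agents take over the Ramsay targets but not, explicitly, the wean steps. The lorazepam and morphine option for ECMO in section 7.12 has no Ramsay 6 wean, but it is optional, so ECMO children kept on midazolam and fentanyl remain under 7.5. A score of 6 is tolerated elsewhere: the midazolam loading target and the ECMO morphine bolus target are both open-ended above 5.

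**The case against.** The strongest reply is that planned paralysis is already covered. The four-hour hold is set to match the time to cool, and paralysis normally ends when the child is cooled. What remains is as-needed blockade, plus about half an hour for slow coolers. Several other points support this side:

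- Children are comatose at entry (section 10.2.2), so a true 6 may be common and the wean rule has a real purpose.
- A clinician who has just paralysed a child may well treat the score as not assessable.
- Section 7.5 allows intermittent doses on top of the infusions.
- The three drugs are recommended, not required.
- Section 12.2 promises a manual of operations and training, neither of which is shown.
- In resistant shivering the rates may already have been raised, so the first cut may be nearer 25% or 33% than 50%.
- The open-ended targets for loading and ECMO boluses are not maintenance targets, so they do not contradict the 7.5 wean rule.

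Most of this stands as a limit on size. It does not remove the problem. As-needed blockade is written into the protocol and the rule has no exception for it. Intermittent doses cannot be guided by Ramsay in a paralysed child. Coma at entry does not make the score valid under blockade, and eligibility excludes only motor scores of 5 and 6, so children with lesser motor responses are enrolled. Reading the rule by its purpose means asking staff to set aside a directive sentence, and a manual that did so would contradict the protocol.

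**Conclusion.** The concern holds. Followed literally, sections 7.5.1 and 7.5.2 direct the wrong action in a child blocked after hour 4. The first step cuts both drugs by 50% from the starting rates, or by 33% or 25% if the rates had been raised by one or two increments, which is an assumption. Complete withdrawal is not ordered, because stopping requires a score of 5.

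The conclusion rests on the inference that a blocked child scores 6, which follows from the protocol's own descriptions of 5 and 6. Exposure is only the time a child is actually blocked after hour 4. The protocol gives neither that time nor the number of children, so no frequency can be stated. Endpoints, analysis and sample size are untouched. It should be fixed because it is a stated rule that misfires on patient safety, not a detail left for elsewhere.

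**What to change.** Add a sentence to sections 7.5.1, 7.5.2 and 7.6: in both arms, Ramsay-triggered weaning is suspended while neuromuscular blockade is in effect. Infusions stay at no less than the current rate until the block has worn off and the score can be assessed, unless the clinical team lowers them for a documented reason such as hypotension. Apply the same principle to any substitute agent titrated to Ramsay.

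The cost is wording in three sections and a note in the manual and training. The downside is slightly longer sedative exposure in children blocked after hour 4. No new procedure is needed and the sample size does not change.
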